7 PROGRAMMING SPECIFICATIONS

Statistical analyses will be performed using SAS® (Cary, NC) version 9.4 or above. All available data will be presented in patient data listings, which will be sorted by Cohort, site number, unique patient identifier and where appropriate, visit number and visit/assessment date. For the interim safety and efficacy analysis, efficacy-related listings that may unblind treatment assignment for individual patients will not be delivered to the Sponsor unless the Sponsor requested such and documented accordingly.

The programming specifications, including the mock-up validity listings, analysis tables, figures, and data listings, as well as the derived database specifications, will be prepared in stand-alone documents.

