8.3. Randomization and Blinding

Cohorts 1 and 2 are directly assigned to the 20 mg/kg dose of SRK-015 while Cohort 3 patients will be randomized (1:1) in a double-blind manner to receive either 2 mg/kg or 20 mg/kg SRK-015 via an Interactive Web-based Randomization System (IWRS). Use of the IWRS will be outlined in the Study Operations Manual and in the IWRS quick reference guide.

The Sponsor, patients, caregivers, Investigators, and site personnel, with the exception of the Pharmacist, will be blinded to Cohort 3 SRK-015 dose level assignments as specified here. The site Pharmacist will remain unblinded throughout the duration of the study. The Sponsor will be blinded to individual efficacy data until prespecified interim analyses are performed (see [Section 11.4](#)). The Sponsor will remain blinded to efficacy data not included as part of the interim analyses until the Treatment Period database lock or deemed necessary by the SST. Select personnel of the Sponsor (e.g., Lead Clinical Research Associate and auditors) will have access to efficacy data to ensure study oversight.

For unblinding procedures refer to [Section 10.7.1.5](#). Based on interim analysis at 6 months (Day 168), which was supported by the 12-month analysis (Day 364), any Cohort 3 patients who were randomized to receive low-dose (2 mg/kg) SRK-015 will be re-assigned to receive high-dose (20 mg/kg) SRK-015 after completion of the Treatment Period (see [Section 6.2](#)).

Original blind designation will be maintained. In accordance with [Section 6.3.1](#), the SST reviews will not include any efficacy data.

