2.2.2 Randomization and Blinding

Patients in Cohorts 1 and 2 are directly assigned to the 20 mg/kg dose of SRK-015 while Cohort 3 patients will be randomized (1:1) without stratification in a double-blind manner to receive either 2 mg/kg or 20 mg/kg SRK-015 via an Interactive Web-based Randomization System (IWRS). Use of the IWRS will be outlined in the Study Operations Manual and in the IWRS quick reference guide.

The Sponsor, patients, caregivers, Investigators and site personnel, with the exception of the Pharmacist, will be blinded to Cohort 3 SRK-015 dose level assignments. The site Pharmacist will remain unblinded throughout the duration of the study. The Sponsor will be blinded to individual efficacy data and cohort-level efficacy results until prespecified interim analyses are performed and will only be unblinded to the cohort-level efficacy results at the safety and efficacy interim analysis. The Sponsor will remain blinded to individual efficacy data until the Treatment Period

database lock or deemed necessary by the Safety Surveillance Team (SST). A list of personnel who may be granted access to the efficacy data from the Sponsor side to perform data monitoring/quality check will be documented. As PK/PD data can be inherently unblinding, the persons who perform the PK/PD interim analyses and review the individual data will be unblinded and documented.

In the event of a drug-related, serious, unexpected adverse event (AE), Medpace (the clinical research organization for the study) may provide a Cohort 3 patient's dose level to the Sponsor for the purpose of regulatory authority agency reporting.

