3.2.2 Per-Protocol (PP) Population

The PP Population is defined as all patients in the ITT Population who completed the study with no major protocol deviations that may impact the primary efficacy assessment. The PP Population will be a secondary population for analysis of the primary efficacy endpoint. Major protocol deviations that may impact the primary efficacy assessment may include but are not limited to:

- Failed to meet eligibility criteria;
- Took the wrong study drug (i.e., did not take the randomized study drug or full dose);
- Had study drug compliance <80%;
- Took a restricted concomitant medication; or
- Failed to complete the efficacy assessment at certain time points.

A list of patients with major protocol deviations leading to exclusion from the PP Population will be finalized prior to the Sponsor's review of the efficacy data and before unblinding of the randomized treatment assignments.

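### SAP section 7 lets the Sponsor obtain, on its own documented request, interim listings that could reveal individual Cohort 3 dose, in conflict with the blind set out in SAP 2.2.2 and Protocol 8.3

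*Combined protocol and SAP*

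**What the plan says.** SAP section 7 (Programming Specifications) states, for the interim safety and efficacy analysis, that efficacy listings which could reveal an individual patient's dose "will not be delivered to the Sponsor unless the Sponsor requested such and documented accordingly". It names no approver, purpose or recipient, and does not refer to SAP 2.2.2.

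SAP 2.2.2 (Randomization and Blinding) puts the Sponsor among the parties who "will be blinded to Cohort 3 SRK-015 dose level assignments". At the interim the Sponsor "will only be unblinded to the cohort-level efficacy results at the safety and efficacy interim analysis". For patient-level results: "The Sponsor will remain blinded to individual efficacy data until the Treatment Period" database is locked, or unless the SST considers release necessary. Three further exceptions are narrow: a documented list of Sponsor-side personnel with access to efficacy data for monitoring and quality checks, documented analysts for the PK/PD interim, and release of a patient's dose for regulatory reporting of a drug-related, serious, unexpected event.

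Protocol 8.3 lists the Sponsor alongside patients, caregivers and site staff, who, "with the exception of the Pharmacist, will be blinded to Cohort 3 SRK-015 dose level assignments as specified here". On efficacy data it is looser than the SAP. Individual data are blinded only until the interim analyses are performed, data outside the interim stay blinded to lock or SST need, and selected oversight staff have access.

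SAP 3.2.2 requires the list of PP exclusions to be final before the Sponsor reviews efficacy data and "before unblinding of the randomized treatment assignments".

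**The concern.** Section 7 makes the party that is meant to be blind the one that opens the blind. A documented request leaves a trail, but it is not an independent approval. The same SAP is stricter with comparable material: section 5.1.1 confines individual PK data and Cohort 3 assignments to designated personnel and has the results presented in aggregate.

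Cohort 3 is the only randomised part of the trial (2 versus 20 mg/kg, planned at 10 per arm). A dose-linked listing from the interim would stay informative until lock, because the assignment does not change during the Treatment Period. Decisions open in that time could then be taken with knowledge of dose and early outcome. The clearest is PP membership, since the qualifying deviations in SAP 3.2.2 are given as an open list. A second possibility is SAP 3.1.7.3, under which three or more consecutive doses missed because of COVID-19 site restrictions turn later assessments into missing data in the main ITT analysis.

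**Working it through.** **1. The provisions side by side**

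| Provision | Individual interim efficacy data | Cohort 3 dose assignment |
|---|---|---|
| SAP 7 | Listings that could reveal dose are released if the Sponsor asks and records it | Same listings, same rule |
| SAP 2.2.2 | Withheld to lock or SST need; documented monitoring and quality-check list excepted | Withheld; documented PK/PD analysts and serious unexpected event reporting excepted |
| Protocol 8.3 | Withheld only until the interim; oversight staff excepted | Withheld; no release at the interim is stated |

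On individual efficacy data, the conflict is within the SAP (7 against 2.2.2), and Protocol 8.3 is a third, looser rule. On dose assignment, SAP 7 conflicts with both SAP 2.2.2 and Protocol 8.3. The words 'as specified here' in Protocol 8.3 do not resolve this, because its interim release concerns efficacy data, not dose.

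**2. Timing**

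- Per patient, Day 168 to Day 364 is 364 − 168 = 196 days, with 7 of the 13 Treatment Period doses (Days 168, 196, 224, 252, 280, 308, 336) still to be given from Day 168 on.
- Protocol 6.2 gives an interim cutoff of 20 August 2020 and a 12-month database lock of 19 January 2021: 11 + 30 + 31 + 30 + 31 + 19 = 152 days. I take that lock to be the Treatment Period lock.
- SAP 2.2.1 already reports the dose reassignment that followed the interim, and SAP 6 cites protocol version 4.0 of 13 November 2020. The present SAP text is therefore no earlier than that date, which is 17 + 31 + 19 = 67 days before lock. It speaks of the 12-month analysis as still to come. The clause may thus have been in force before lock, but the documents do not show for how long.

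**3. The plan's own figures for the dose comparison**

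Inputs (SAP 2.2.3, Protocol 11.3): 10 per arm, two-sided 5%, SD of HFMSE change 2.5.

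- Noncentral-t power with 18 df at effect size 1.325: 0.8000. The stated 80% reproduces.
- Smallest difference reaching p = 0.05, which is also the 95% CI half-width: t(0.975, 18) × √(2/10) × SD = 2.101 × 0.447 × 2.5 = 2.35 points. The plan states 2.4.

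**4. What one exclusion could do (illustrative)**

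Removing one value at distance d from the mean of n shifts the mean by d/(n − 1). With n = 10 and SD 2.5:

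| Distance from arm mean | Shift in arm mean | Share of 2.35 |
|---|---|---|
| 1 SD (2.5 points) | 2.5/9 = 0.28 | 12% |
| 1.5 SD (3.75 points) | 3.75/9 = 0.42 | 18% |
| 2 SD (5 points) | 5/9 = 0.56 | 24% |

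The distances are assumptions. In the PP population such a removal is direct. In the ITT population only the COVID-19 rule could set aside observed data.

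**The case against.** The strongest reply is that the mismatch is minor wording. Non-delivery is the default, the clause covers only listings that might unblind, and a request has to be documented. Sponsor-side access to efficacy data without lock or SST already exists through the monitoring list in SAP 2.2.2 and the oversight access in Protocol 8.3, and the protocol lifts the blind on individual efficacy data at the interim. All of this stands, and it narrows the conflict. It does not remove it: the existing access is for stated purposes and is not described as dose-linked, whereas section 7 concerns exactly the listings that could expose dose and sets no limit on who may receive them.

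The consequences are also limited. SAP 3.1.5 rules out formal testing. The Cohort 3 primary endpoint is change within the high-dose arm, with the dose difference explored descriptively (SAP 3.4.3.1). PP is secondary, and a sensitivity analysis using all data is already planned beside the COVID-19 rule (SAP 3.2.1). Patients, investigators and site staff other than the pharmacist stay blinded. The Sponsor was meant to see interim efficacy at cohort level, and the greater high-dose improvement supported the extension dose change (Protocol 4.7). What section 7 adds is individual assignment linked to outcome. These points stand and keep the concern modest.

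A reader might infer that section 7 overrides the PP safeguard. It does not: SAP 3.2.2 still requires the list to be final first, and section 7 does not waive that. The weakness is that a request could break the required order without any check.

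**Conclusion.** The inconsistency is real. Following SAP 7 as written could break the blind that SAP 2.2.2 and, for dose, Protocol 8.3 set out. The exposure is to judgement calls open before lock, chiefly the PP list and possibly COVID-19 attribution. In the assumed examples, one influential exclusion moves an arm mean by 0.28 to 0.56 points, or 12% to 24% of the CI half-width. This rests on the plan's illustrative SD of 2.5, 10 patients per arm, and the premise that people who received such a listing would also take part in those decisions. That premise is an inference, because the documents do not say who decides.

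Two stronger readings are not supported. One is that the blind was in fact broken, or that all 20 Cohort 3 patients were affected: no document shows that a listing was requested. The other is that the trial's primary result or a Type I error rate is compromised: the main population is ITT and nothing is formally tested. No sample size or power figure changes.

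**What to change.** - In SAP 7, delete the exception for Sponsor requests. State that before Treatment Period database lock no listing linking a Cohort 3 patient to dose goes to the Sponsor, except to named, documented, firewalled people who take no part in deviation, PP or COVID-19 exclusion decisions.
- Keep the documented monitoring and quality-check access to efficacy data, without dose.
- Align SAP 7, SAP 2.2.2 and Protocol 8.3 on what the Sponsor may see at the interim. Do not rely on the SST alone as gatekeeper: its core includes two Sponsor staff and its reviews exclude efficacy data (Protocol 6.3.1).
- Because the interim has already been run, state in the CSR whether any such listing was requested, when, and by which roles, and whether the PP list was final beforehand. This is now the most useful part of the remedy.

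The cost is a few sentences across the two documents and one CSR statement. The Sponsor gives up discretionary early access to individual dose-linked listings.
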